The classic 3 + 3 design will be conducted as follows. Initially, 3 patients will be enrolled to a cohort; the occurrence of a single drug-related DLT in one of these 3 patients will prompt enrollment of up to an additional 3 patients to that same cohort i.e., 3 + 3. When more than 1 DLT occurs in  $\leq$  6 patients in a dosing cohort, dose escalation will be stopped and this dose level will be identified as the non-tolerated dose. Doses between the non-tolerated dose and the preceding lower dose, where  $\leq$  1 DLT occurred, may be explored to define the MTD. This strategy allows for a rigorous determination of MTD, especially if the dose increase that resulted in determination of the non-tolerated dose is relatively large (i.e.,  $>$  50%).

At any time during the study, the Sponsor and Investigators may request that cohorts should be enlarged or that exploration of intermediate doses between 2 planned escalation steps should be explored. Such requests will be discussed with the Sponsor and Medical Monitor, and should be based on all data existing at that time, including determinations of pharmacokinetics, pharmacodynamics, and cumulative toxicity. Before each escalation, investigators will be consulted to ensure that all involved agree with the escalation decision.

In addition, once the RP2D is defined, intra-patient dose escalation to the RP2D will be allowed after a patient has completed at least 1 cycle at their assigned dose and only if the patient has experienced no toxicity above Grade 1, upon request by the PI and discussion with the Medical Monitor and the Sponsor.

Part 2 – Cohort-expansion Phase: Additional patients with particular tumor types and/or cancers harboring specific genetics will be recruited for treatment at the Recommended Phase 2 Dose (RP2D). Patients must have measurable disease by RECIST 1.1. Patients will receive twice daily oral doses of BVD-523 in 21-day treatment cycles until disease progression, unacceptable toxicity, or another withdrawal criterion is met (Section 7.2). Treatment cycles will occur consecutively without interruption except when necessary to manage toxicities.

Total enrollment for Part 2 is targeted at approximately 105 evaluable patients. Patients will be enrolled into 1 of 7 treatment groups. Group assignments are made according to the following disease characteristics, which correspond to specific inclusion and exclusion criteria for Part 2.

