**Table 3.1. Study Medication Dosing and Pharmacokinetics/Pharmacodynamics Chart**

	Study Days			
	1	8	15	22
BVD-523 Dosing 	X	X	X	X
Pharmacokinetics Sampling	X		X	X
Pharmacodynamics Sampling 	X		X	

 Dosing is twice daily in 21-day cycles until disease progression. Patients may be treated beyond disease progression for additional 21-day cycles at the same dose level at the Investigator’s discretion. However it is particularly important in patients for which FDA approved BRAF and/or MEK inhibitors are indicated that BVD-523 treatment NOT be continued beyond tumor progression. Study medication for a week of dosing will be dispensed at each visit (± 1 day for Cycles 1 and 2, ± 2 days for later cycles). For treatment cycles after Cycle 2, study medication for 3 weeks of dosing will be dispensed. Additional medication may be dispensed to ensure uninterrupted dosing, if needed.

 Pharmacodynamic sampling should only be completed in those patients that consent to optional biopsy. Those patients that do not consent to this collection do not need to have pharmacodynamics samples taken.

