## **4 SELECTION OF PATIENTS**

### **4.1 NUMBER OF PATIENTS**

In this Phase 1 study up to 40 patients with advanced solid tumors will be enrolled in Part 1. One to six patients per treatment cohort will be assigned to receive sequentially higher oral doses of BVD-523.

The purpose of Part 2 of this first in human research is to document that there is some evidence of a response. Upon completion of Part 1 of this study, up to approximately 105 evaluable patients with certain cancer types and/or characterized genetics will be assigned to 1 of 7 treatment arms and treated with the RP2D determined in Part 1 (which may be the same or lower than the MTD). The observation of DLTs in more than 33% of patients in any Part 2 cohort with at least 6 patients enrolled at any time during Part 2 will trigger temporary stopping of patient enrollment and revision of the definition of the MTD and potentially RP2D in the specific cohort. Subsequent patients will be treated with a dose lower than the initial MTD and this dose will be determined in discussion with the Clinical Investigators, the Medical Monitor, and the Sponsor.

Enrollment of up to 15 evaluable patients in each cohort provides an 80% probability of seeing at least one positive response if the true response rate is at least 10%. Allowing for a low response rate in these patient cohorts is appropriate based on unmet medical need.

In Part 2 of the study, patients who withdraw at any time preceding the 1st protocol-specified tumor measurement evaluation at the end of Cycle 2 (except for study drug-related AE) will be replaced.

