### 7.2 EARLY DISCONTINUATION OF INDIVIDUAL PATIENTS

Patients are to be withdrawn from the study for any of the following reasons:

- Withdrawal of informed consent
- Disease progression (at the discretion of the PI). However it is particularly important in patients for which FDA approved BRAF and/or MEK inhibitors are indicated that BVD-523 treatment NOT be continued beyond tumor progression.
- Unacceptable toxicity
- Changes in the patient's condition render the patient unacceptable for further treatment in the judgment of the PI
- Patient non-compliance as assessed by the investigator
- Patient has a positive serum pregnancy test (withdrawal is required)
- Patient is lost to follow-up

Patients will also to be withdrawn at any time if the investigator concludes that it would be in the patient's best interest for any reason. Protocol violations do not lead to patient withdrawal unless they constitute a significant risk to the patient's safety.

Patients can voluntarily withdraw from the trial for any reason at any time. They are to be considered withdrawn if they state an intention to withdraw, fail to return for visits, or became lost to follow up for any reason.

In Part 1 of the study, patients who withdraw at any time preceding the last visit of Cycle 1 (Day 22) will constitute an early discontinuation and must be replaced in order to ensure proper data accrual for dose escalation decisions. A patient who experiences a DLT in Course 1 and withdraws before Day 22 either because of the toxicity or otherwise, will nonetheless have that DLT counted in the assessment of potential cohort expansion and/or dose escalation (see Table 3.2).

In Part 2 of the study, patients who withdraw at any time preceding the 1st protocol-specified tumor measurement evaluation at the end of Cycle 2 (except for study drug-related AE) will be replaced.

The investigator must determine the primary reason for a patient's withdrawal from the study and record this information on the eCRF.

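### Part 2 replaces patients withdrawn for progression or deterioration before the first scan, and the per-protocol response tables leave them out, so the reported response rate overstates the rate among treated patients.

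*Protocol*

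**What the plan says.** **Replacement.** Protocol 4.1 and 7.2 give the same Part 2 rule: patients who withdraw before the first "tumor measurement evaluation at the end of Cycle 2 (except for study drug-related AE) will be replaced". A study drug-related AE is the only exception. The withdrawal reasons in 7.2 include "Disease progression (at the discretion of the PI") and a change in condition that makes further treatment unacceptable. Death is named neither in the rule nor in that list.

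**Sample size.** Protocol 4.1 states: "Enrollment of up to 15 evaluable patients in each cohort provides an 80% probability of seeing at least one positive response". The figure assumes a response rate of 10% or more. No section defines what makes a patient evaluable for response.

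**Timing.** Patients are treated "in 21-day treatment cycles until disease progression, unacceptable toxicity, or another withdrawal criterion is met", so the first evaluation falls after two 21-day cycles. A footnote to Table 3.1 adds: "Patients may be treated beyond disease progression for additional 21-day cycles", at the investigator's discretion. It also stresses that this should not happen where approved BRAF and/or MEK inhibitors are indicated.

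**Analysis.** Protocol 10.2.3 and SAP 5.3 define the per-protocol (PP) population by completion of the first tumor evaluation, again with drug-related AE as the only exception. SAP Section 9 opens by promising efficacy analyses on both mITT and PP, then tabulates response on PP. Every efficacy display listed in SAP Section 14, for both parts, is PP. SAP 5.2 defines mITT as all dosed patients. SAP 5.3 calls PP analyses exploratory.

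**The concern.** A patient withdrawn in the first six weeks because the tumor has grown or the disease has worsened has had an outcome: the treatment did not produce a response. The plan handles that patient as if the information were missing, filling the place with someone else and leaving the patient out of the response table.

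The information may well exist. Section 6.8 calls for tumor measurement by physical examination on the first day of each cycle, and the End of Treatment visit (5.2.6) requires a tumor assessment if the last scan was more than 21 days earlier. Progression can therefore be documented in a patient who is then replaced.

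The protocol does keep informative exits elsewhere. Drug-related AE withdrawals are not replaced in Part 2, and under 7.2 a Part 1 patient who has a DLT and withdraws still has that DLT counted. Early disease failure has no such provision.

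At stake is the response percentage for each of the seven groups. With at most 15 patients in a group, omitting two or three failures changes it visibly.

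**Working it through.** **Step 1. Reproduce the plan's figure.** Inputs from Protocol 4.1: n = 15 evaluable patients, true response rate 10%.

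P(at least one response) = 1 − (1 − 0.10)^15 = 1 − 0.2059 = 0.794.

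This agrees with the stated 80% after rounding. (With n = 16 it would be 0.815.)

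**Step 2. Effect on the reported rate.** Let f be the fraction of treated patients withdrawn before the first evaluation for progression, deterioration or (by inference) death. The documents give no value, so f = 10%, 20% and 30% is an assumed range. Assume that none of these patients responds, and let p be the response rate among treated patients. Then:

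- rate reported with early failures removed = p / (1 − f)
- treated-patient rate implied by a 10% evaluable rate = 0.10 × (1 − f)
- treated patients needed to fill 105 evaluable places = 105 / (1 − f)

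| f | Reported rate when p = 10% | Treated rate when evaluable rate = 10% | Treated patients for 105 evaluable |
|---|---|---|---|
| 10% | 0.10/0.90 = 11.1% | 9% | 117 |
| 20% | 0.10/0.80 = 12.5% | 8% | 131 |
| 30% | 0.10/0.70 = 14.3% | 7% | 150 |

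For a single group, 15 evaluable places take about 17, 19 or 22 treated patients (15/(1 − f), rounded up). Two responders would be shown as 2/15 = 13.3%, against 2/17 = 11.8%, 2/19 = 10.5% or 2/22 = 9.1% of those treated.

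**Step 3. Does the all-dosed population cure it?** Suppose a group is treated until 15 patients are evaluable, so that the number treated, N, is random. The expected all-dosed rate is [0.10/(1 − f)] × E(15/N), with N negative binomial. It is 10.1%, 10.1% and 10.2% for f = 10%, 20% and 30%. The replacement rule alone therefore leaves almost no bias when every dosed patient is in the denominator. The inflation in Step 2 arises when replaced patients are dropped from the denominator, as in the PP tables.

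**Step 4. Effect on the chance of at least one response.** With p = 10% among treated patients, 1 − (1 − p/(1 − f))^15 gives 82.9%, 86.5% and 90.1%. Treating 15/(1 − f) unselected patients at a 10% rate, 1 − 0.9^(15/(1 − f)), gives 82.7%, 86.1% and 89.5%. Nearly all of the rise above 79.4% comes from treating more patients.

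Read the other way, if 10% is the evaluable rate, the chance of at least one response in 15 treated patients is 1 − (1 − 0.10(1 − f))^15 = 75.7%, 71.4% or 66.3%.

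**The case against.** The strongest reply is that the SAP already contains the remedy. Its mITT population keeps every dosed patient, Section 9 promises efficacy on it, PP results are labelled exploratory, and Step 3 shows the mITT rate to be almost unbiased. This stands as far as it goes. But SAP 5.3 and the tabulation sentence in Section 9 assign response to PP, and Section 14 lists no mITT response table, so the displays as specified would not show that rate.

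Several stronger readings are tempting, and the documents do not support them.

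- *The 80% is wrong.* It is written for evaluable patients and reproduces. If the treated-patient rate is 10%, replacement raises the chance of a response above 79.4%.
- *The bias acts whichever population is analysed.* Step 3 shows that it does not.
- *The 15 are patients who survived six weeks without progressing.* Drug-related AE withdrawals keep their places, progression found at the first evaluation counts, and a patient kept on treatment after early progression is not replaced. The group sizes are also ceilings.
- *Patients who die are expressly replaced.* This is only an inference from there being a single exception.

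It is also fair to say that Part 2 seeks only some evidence of response. No inferential test or formal efficacy analysis is planned, and entry requires ECOG 0 or 1 and a predicted life expectancy of at least three months, so f may be small. This limits the consequences. It does not justify a denominator that depends on outcome.

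**Conclusion.** The point holds for the reported response percentage. As written, the plan removes from the PP denominator patients withdrawn early because their disease progressed or they deteriorated. At a 10% rate among treated patients, the tabulated rate would be 11.1% to 14.3% for f between 10% and 30%. A tabulated 10% would correspond to 9% to 7% of those treated.

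These sizes rest on the assumed f and on no early leaver being a responder. The true size is unknown and may differ between groups. The direction is not in doubt so long as early leavers respond less often than those who remain.

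The 80% statement is sound for 15 evaluable patients and should not be read as describing all patients treated. The defect lies in the replacement rule and the PP definition together, with no mITT response table listed to offset them.

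**What to change.** 1. In Protocol 4.1 and 7.2, define evaluable for response. Widen the exception so that withdrawal for disease progression, clinical deterioration or death before the first evaluation is not replaced and counts as non-response. Replace only patients who leave for reasons unrelated to disease or drug.
2. Make the same change in the PP definitions (Protocol 10.2.3, SAP 5.3). Editing 4.1 and 7.2 alone would not change the tabulated rate, because PP would still require a completed evaluation.
3. Add best overall response tables by group on the all-dosed mITT population to SAP Section 14, in line with the opening of Section 9.
4. State that the 10%/80% sentence refers to evaluable patients so defined.
5. Report the number replaced, with reason, for each group. The disposition table in SAP 8.1 already gives withdrawal reasons by group, so this adds little.

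The cost is wording in two protocol sections and two PP definitions, a few added tables, and a slightly less favourable response rate. Fewer replacement patients are needed. If the treated-patient rate is 10%, the chance of at least one response among 15 returns to the stated 79.4%, instead of the 82.9% to 90.1% that extra enrollment would give. Nothing changes in treatment or in who may enter.

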### **4.2 RECRUITMENT**

Three to 10 study centers will enroll up to 40 patients for Part 1.

In addition to the sites supporting Part 1 studies, sites may be added (up to 15 total sites) to enroll up to approximately 105 evaluable patients for Part 2 of the study.

### **4.3 INCLUSION CRITERIA**

Patients eligible for inclusion in this trial have to fulfill all of the following criteria:

1. Provide signed and dated informed consent prior to initiation of any study-related procedures that are not considered standard of care (SOC).
2. Male or female patients aged  $\geq 18$  years.
3. Patients with metastatic or advanced-stage malignant tumor, confirmed histologically, for whom no therapy exists that would be curative.
4. ECOG performance status of 0 (fully active, able to carry out all pre-disease activities without restriction) or 1 (unable to perform physically strenuous activity but ambulatory and able to carry out work of a light or sedentary nature), measured within 72 hours before the start of treatment.

5. Predicted life expectancy of  $\geq 3$  months.
6. Adequate renal function [creatinine  $\leq 1.5$  times ULN (upper limit of normal)] or GFR of  $\geq 50$  mL/min.
7. Adequate hepatic function [total bilirubin  $\leq 1.5$  times ULN; AST (aspartate transaminase) and ALT (alanine transaminase)  $\leq 3$  times ULN or  $\leq 5$  times ULN if due to liver involvement by tumor].
8. Adequate bone marrow function (hemoglobin  $\geq 9.0$  g/dL; platelets  $\geq 100 \times 10^9$  cells/L; absolute neutrophil count  $\geq 1.5 \times 10^9$  cells/L).
9. Adequate cardiac function,  $\geq$  institutional lower limit of normal e.g., left ventricular ejection fraction (LVEF) of  $> 50\%$  as assessed by multi-gated acquisition (MUGA) or ultrasound/echocardiography (ECHO); corrected QT interval (QTc)  $< 470$  ms.
10. Contraception:
  - For women: Negative pregnancy test for females of child-bearing potential; must be surgically sterile, postmenopausal (no menstrual cycle for at least 12 consecutive months), or compliant with a contraceptive regimen during and for 3 months after the treatment period. Abstinence is not considered an adequate contraceptive regimen.
  - For men: Must be surgically sterile, or compliant with a medically approved contraceptive regimen during and for 3 months after the treatment period.
11. Willing and able to participate in the trial and comply with all trial requirements.
12. For Part 2 of the Study ONLY:
  - Patient must be diagnosed with specific tumor types and histologies (Section 3.1.2).
  - Patient must bear tumors that harbor specific classes of genetic mutations.
  - Patients must have measurable disease by RECIST 1.1.

#### 4.4 EXCLUSION CRITERIA

Patients who fulfill one or more of the following criteria will not be eligible for inclusion in this trial:

1. Gastrointestinal (GI) condition that could impair absorption of study medication (specific cases e.g., remote history of GI surgery, may be enrolled after discussion with the medical monitor), or inability to ingest study medication.
2. Uncontrolled or severe intercurrent medical condition.
3. Known uncontrolled brain metastases. Stable brain metastases either treated or being treated with a stable dose of steroids/anticonvulsants, with no dose change in the previous 4 weeks, can be allowed.
4. Any cancer-directed therapy (chemotherapy, hormonal therapy, biologic or immunotherapy, etc.) within 28 days or 5 half-lives, (whichever is shorter). Patients previously treated with radiotherapy must have recovered from the acute toxicities associated with such treatment.
5. Major surgery within 4 weeks prior to first dose.
6. Any use of an investigational drug within 28 days or 5 half-lives (whichever is shorter) prior to the first dose of BVD-523. A minimum of 10 days between termination of the investigational drug and administration of BVD-523 is required. In addition, any drug-related toxicity except alopecia should have recovered to Grade 1 or less.

7. Pregnant or breast-feeding women.
8. Any evidence of serious active infections.
9. Any important medical illness or abnormal laboratory finding that would increase the risk of participating in this study (based on the investigator's judgment).
10. A history or current evidence/risk of retinal vein occlusion (RVO) or central serous retinopathy (CSR).
11. Concurrent therapy with any other investigational agent.
12. Concurrent therapy with drugs known to be strong inhibitors of CYP1A2, CYP2D6 and CYP3A4, or strong inducers of CYP3A4 (for list of non-permitted drugs, see [Appendix 1](#)).
13. Concomitant malignancies or previous malignancies with less than 2 years disease-free interval at the time of enrollment (except non-melanoma skin cancer, cervical cancer in situ, prostate cancer with undetectable PSA). Other concurrent malignancies that are indolent and do not require active treatment must be discussed with the medical monitor prior to enrollment.

## 5 STUDY PLAN AND PROCEDURES

This clinical study will consist of 2 parts. In Part 1, patients with advanced solid tumors will receive sequentially higher oral doses of BVD-523.

In Part 2, patients will be assigned to 1 of 7 treatment groups based on specific tumor and clinical characteristics and will be treated at the Recommended Phase 2 Dose determined in Part 1.

To characterize the pharmacokinetic properties of BVD-523 in patients, blood, urine, and tissue biopsy (as indicated) samples will be obtained/analyzed during Cycle 1 of Part 1, and during additional cycles in Part 1 and/or Part 2 as indicated.

Multiple pharmacodynamics biomarkers will be used to measure response to drug treatment, including evaluation of pRSK, pERK, Ki67, Caspase-3, and circulating tumor DNA. Biomarker samples/measurements will be obtained during Cycle 1 of Part 1, and during additional cycles in Part 1 and/or Part 2 based on accumulated experience (appropriate control samples/measurements will be taken prior to patient receiving their first dose).

Tumor assessments will be made by CT/MRI/Physical Exam prior to dose initiation, at the 1st protocol-specified tumor measurement evaluation at the end of Cycle 2 and then every 2-3 cycles, and at End of Treatment.

All patients will be screened and eligibility determined prior to enrollment and start of study treatment.

### 5.1 STUDY PATIENT NUMBER

In Part 1, up to forty patients are expected to be enrolled.

In Part 2 of the study, up to approximately 105 evaluable patients with measurable disease will be enrolled:

- Group 1: Patients with BRAF mutated cancer, except those with colorectal or non-small cell lung cancers, not previously treated with BRAF and/or MEK inhibitors;  $n \leq 15$
- Group 2: Patients with BRAF mutated colorectal cancer, not previously treated with BRAF and/or MEK inhibitors;  $n \leq 15$
- Group 3: Patients with BRAF mutated melanoma who have progressed or are refractory to BRAF and/or MEK inhibitors;  $n \leq 15$
- Group 4: Patients with NRAS mutated melanoma, not previously treated with BRAF and/or MEK inhibitors;  $n \leq 15$
- Group 5: Patients with MEK mutated cancer, not previously treated with BRAF and/or MEK inhibitors;  $n \leq 15$

- Group 6: Patients with BRAF mutated non-small cell lung cancer, not previously treated with BRAF and/or MEK inhibitors;  $n \leq 15$
- Group 7: Patients with ERK mutated cancer, not previously treated with BRAF and/or MEK inhibitors;  $n \leq 15$

## 5.2 DESCRIPTION OF STUDY VISITS FOR PART 1

Procedures performed in the first cycle are specified in Table 6.1. Patients receiving multiple cycles of treatment will not have blood drawn for pharmacokinetic and pharmacodynamic measurements after Cycle 1 unless additional pharmacokinetic and pharmacodynamic data are deemed necessary after initial analysis.

